Endostapler Hemostasis Study Protocol

September 9, 2019

A proposed study using AEON™ Endostapler Handles and Reloads

(Lexington Medical, Inc., Billerica, Massachusetts)

Principal Investigator:

[name] (surgeon)

Co-Investigator(s):

[name] (surgeon)

[name] (surgeon)

Research Coordinator:

[name]

Primary Outcome Evaluator:

[name]

SUMMARY

The goal of this prospective, multi-center, post-market study is to measure AEON™ Endostapler performance with the EASY/THICK MODE feature for laparoscopic bariatric surgery against the Echelon Flex™ Powered Stapler system from Ethicon. Stapler performance will be evaluated primarily by incidence and degree of staple line bleeding through a third-party blinded primary outcome evaluator. The study will include 60 total consecutive cases of individuals undergoing a planned laparoscopic sleeve gastrectomy (LSG). The LSG procedure will be performed according to institutional standard-of-care and all subjects will undergo standard preoperative evaluation as well as post-operative care. Relevant data will be collected using the Data Collection sheet which should be filled out following each procedure by a member of the surgical or nursing team.

Enrollment: 60 Subjects Meeting Inclusion/Exclusion Criteria

Investigator Masking: None (Open Label)

Primary Outcome Evaluator Masking: Yes (Surgeon and Device)

Devices: AEON™ Endostapler and Echelon Flex™ Powered Stapler System

LEXINGTON MEDICAL AEON™ ENDOSTAPLER BACKGROUND

The AEON™ Endostapler is comprised of a stapler handle and reloads. The handle may accept multiple reloads of single fire cartridges. The AEON™ Endostapler devices were approved by the United States Food and Drug Administration (FDA) under the 510(k) process. Pertinent applications numbers are K171589 and K173443. Devices will be used pursuant to the indications specified in K171589 and K173443, as well as the general guidelines for use of this device on a prescription basis as outlined by the Federal Food, Drug, and Cosmetic Act (1976), and the Code of Federal Regulations Title 21 Part 800-895.

Approved Indications for Use

The AEON™ Endostapler has applications in general, abdominal, gynecologic, pediatric and thoracic surgery for resection, transection and creation of anastomoses.

Available AEON™ Endostapler Reloads

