Subjects are free to withdraw from the study at any time for any reason. Every effort will be made to determine why any subject withdraws from the study prematurely and this information will be recorded in the Clinical Study Report.

In addition, subjects may be withdrawn from the study by the Principal Investigator in consultation with the Sponsor for the following reasons:

- Adverse event
- Protocol violation
- Loss to follow-up

If a subject withdraws prematurely, all data normally collected by study completion should be collected at the time of premature discontinuation or at the scheduled discharge. All subjects who withdraw from the study with an ongoing adverse event must be followed until the event is resolved or deemed stable. At the discretion of the PI, additional follow up visits may be done for subject safety.

Withdrawn subjects will be replaced, until 60 subjects complete the study.

Primary Outcome Measure:

- Incidence of intraoperative staple line bleeding as measured by the provided bleeding severity scale

Secondary Outcome Measures:

- Incidence of postoperative leakage during one-month monitoring period following procedure
- Incidence of reported device-related adverse events
- Incidence of product malfunction during procedure
- Incidence of intraoperative or postoperative blood transfusion within 72 hours of surgery start time
- Postoperative pain level per standard protocol

Steps and Procedures:

The study will include 60 total consecutive cases, randomized for stapler type: 30 with the AEON™ Endostapler and 30 with Echelon Flex™. Surgeries will be performed by either [name], [name], or [name], with at least 5 surgeries of each stapler brand per surgeon.

All patients will undergo the standard preoperative evaluation pathway. Patients must sign informed consent for the operation.

All firings with the AEON™ Endostapler will be done with EASY/THICK MODE for the purposes of this study and shall conform to the AEON™ Instructions For Use (Appendix C). All firings with the Echelon Flex™ should be done according to the Echelon Flex™ Instructions for Use.

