In order to measure the primary outcome of incidence and degree of staple line bleeding, a third-party blinded primary outcome evaluator will be used. No sutures, cautery or clips shall be applied to the staple line during stapling, unless required at surgeon's discretion. Following the last firing, a member of the surgical or nursing team or the research coordinator present for the case will count 10 seconds and then capture an image with the laparoscope. The visual should be clear and portray the entire length of the staple line. In the event that bleeding from the staple line requires control prior to the last firing, an additional image should be captured before applying sutures, cautery, clips, etc. These photographs will then be sent by the research coordinator to the primary outcome evaluator either electronically or by mail. The primary outcome evaluator will be blinded to both the surgeon and device of each case. Upon receipt of photographs, the evaluator will evaluate staple line bleeding according to a provided bleeding severity scale and record results in the Bleeding Severity Evaluation Sheet (Appendix B). If a case has more than one image associated with it, the primary outcome evaluator will consider all images when selecting a bleeding severity level.

At the end of each case, the surgical team will fill out the relevant sections of the Data Collection Sheet (Appendix A). Case ID is captured as day/month/year, followed by surgery count for the day – e.g. 071619A for the first surgery performed on July 16, 2019.

All typical post-operative care will continue, including immediate post-operative care prior to hospital discharge as well as the standard one-week and one-month post-operative evaluation. At the end of both the one-week and one-month post-operative period, a member of the surgical or nursing team will fill out the relevant sections of the Data Collection Sheet.

There will be no follow up study data collected after this point, however the patients will continue the standard follow up regimen per the physician's practice.

Surgery Locations:

Surgeries will take place at Southern Surgical Hospital ([name]), Crescent City Surgical Centre ([name]), or Avala Hospital ([name]).

Termination of the Study:

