Appendix A – Data Collection Sheet

OR Date: _____ Surgeon: _____

Case ID (e.g. 071619A): _____ Hospital: _____

Stapler Type (Circle): AEON™ Endostapler Echelon Flex™ Powered Stapler System

Patient Medications: _____

Patient Gender: _____ Patient Age: _____ Patient BMI: _____

AEON™ Endostapler	Black 60mm	Purple 60mm	Purple 45mm	Orange 60mm	Orange 45mm	Tan 60mm	Tan 45mm
Quantity Reloads Used							

Echelon FLEX™	Black 60mm	Black 45mm	Green 60mm	Green 45mm	Gold 60mm	Gold 45mm	Blue 60mm	Blue 45mm	White 60mm	White 45mm
Quantity Reloads Used										

Intraoperative Outcomes			
Product malfunction (circle)	Yes	No	N/A
Blood transfusion due to staple line bleeding (circle)	Yes	No	N/A

Surgeon overall satisfaction with the stapler used (circle): Dissatisfied Somewhat dissatisfied Neutral Somewhat satisfied Satisfied

Postoperative Outcomes			
Blood transfusion due to staple line bleeding within 72 hours of surgery start time (circle)	Yes	No	N/A
1 Week			
Dysphagia present (circle)	Yes	No	N/A
Nausea present (circle)	Yes	No	N/A
Weight loss:			
Pain level per standard protocol:			
1 Month			
Postoperative leakage during one-month monitoring period following procedure (circle)	Yes	No	N/A
Reported device-related adverse events (circle)	Yes	No	N/A
If yes, please specify:			

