Appendix B – Bleeding Severity Evaluation Sheet

Evaluation Date: _____

Evaluator: _____

Case ID (e.g. 071619A): _____

**Staple line bleeding according to
Bleeding Severity Scale (circle):**

1	2	3	4	5
No bleeding	Minimal bleeding	Moderate bleeding	Excessive bleeding	Profuse bleeding

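### The wait before the primary-outcome image is an untimed, unrecorded count by someone not stated to be masked, from a loosely stated start, so unequal timing between arms could not be detected

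*Combined protocol and SAP*

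**What the plan says.** The primary outcome is "Incidence of intraoperative staple line bleeding as measured by the provided bleeding severity scale" (Primary Outcome Measure). An evaluator grades it from photographs on the five-level scale in Appendix B.

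Steps and Procedures names the start and the person in these words: "Following the last firing, a member of the surgical or nursing team or the research coordinator present for the case". The timing itself comes next in the same sentence, where the person so named "will count 10 seconds and then capture an image with the laparoscope". A quality requirement is added: "The visual should be clear and portray the entire length of the staple line". If bleeding has to be controlled before the last firing, a further image is taken before control. The evaluator takes every image from the case into account.

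On masking, the Summary declares the study open label for investigators and masked only for the evaluator. Steps and Procedures repeats the second part: "The primary outcome evaluator will be blinded to both the surgeon and device of each case".

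The intraoperative part of Appendix A records malfunction and transfusion, followed by a surgeon satisfaction rating. Appendix B records the evaluation date, evaluator, case ID and severity grade. Neither has a place for the time of the last firing, the time of the image, or the seconds between them.

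**The concern.** The evaluator can grade only what the image shows, and how much blood it shows depends partly on how long the line has been free to bleed. For the final segment, the person doing the count controls that time. That person is in the room, is not stated to be masked, and can be expected to know which stapler is in use.

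Two routes could make the interval differ by arm:

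- **The person counting.** An informal count can run short or long, and knowledge of the device could influence it without any intent.
- **The device.** The two staplers are fired under different instructions: AEON always in EASY/THICK MODE, Echelon Flex under its own Instructions for Use. If the time from the end of firing to release of the tissue differs, the same count gives different free bleeding time, unless the count starts at release.

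If either happened, the arms could score differently even though the staplers bleed equally. Randomization would not prevent this, because the timing is set after allocation. The masked reading would not reveal it, because the evaluator sees the result of the timing and not the timing itself.

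**Working it through.** The plan gives no figure to reproduce. It states no bleeding rate, release time, alpha or power, and the Statistics section says that no formal sample size calculation was done. The main check is therefore textual, followed by two illustrations of what a slip could and could not do.

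**Textual check**

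1. *Start of the count.* It is tied to the last firing. The text does not say whether that means the end of the firing stroke, jaw release, withdrawal of the stapler, or the line coming into view. The start is stated but imprecise.
2. *How it is timed.* It is a count, with no clock and no tolerance.
3. *Who times it.* Someone present for an open-label case. Masking is specified only for the evaluator.
4. *What happens if the whole line is not visible at 10 seconds.* The plan does not say whether the timing rule or the whole-line rule gives way.
5. *What is recorded.* Neither form records any time relating to the image.
6. *The extra image before bleeding control.* No wait is stated for it.

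Items 1 to 3 make unequal timing possible. Item 5 makes it undetectable and uncorrectable.

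**Illustration 1: what share of exposure a slip represents**

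Against the stated wait, 1 s / 10 s = 10% and 5 s / 10 s = 50%. But the image must show the whole line, and the line is built from several firings: the handle takes multiple reloads, and Appendix A counts the reloads used. Only the last segment has about 10 seconds of exposure. Assume five firings one minute apart (an assumption; the plan gives neither number):

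| Segment | Exposure at image (s) | 5 s slip as share |
|---|---|---|
| 1 | 250 | 2.0% |
| 2 | 190 | 2.6% |
| 3 | 130 | 3.8% |
| 4 | 70 | 7.1% |
| 5 (last) | 10 | 50% |

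Mean exposure is (250 + 190 + 130 + 70 + 10) / 5 = 130 s, and 5 / 130 = 3.8%. The 50% figure belongs to the last segment alone.

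**Illustration 2: a limiting case for the comparison**

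Suppose, against the point just made, that all visible bleeding starts at the last firing. Assume identical devices, 30 cases per arm (from Steps and Procedures), bleeding scored yes or no, a two-sided Fisher exact test at 0.05, and chance of visible bleeding by t seconds = 1 − (1 − p)^(t/10), where p is the assumed incidence at 10 s. One arm is imaged consistently at 15 s and the other at 10 s:

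| p at 10 s | Incidence at 15 s | Shift (points) | False significance, equal timing | False significance, 15 s v 10 s |
|---|---|---|---|---|
| 20% | 1 − 0.8^1.5 = 28.4% | 8.4 | 2.2% | 7.0% |
| 40% | 1 − 0.6^1.5 = 53.5% | 13.5 | 2.6% | 12.3% |
| 60% | 1 − 0.4^1.5 = 74.7% | 14.7 | 2.6% | 15.4% |

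This shows that a sustained difference of 5 seconds could matter if bleeding were governed by the final wait. It does not estimate the effect in this trial, because earlier segments have longer exposure.

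**The case against.** The strongest case on the other side has five parts.

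- **The start is given.** A reader might infer that the count has no defined start. That is not so: the sentence opens by tying it to the last firing. What stands is only that the exact event is not named.
- **The rule is common to both arms.** The same 10 seconds applies to each stapler. Stapler type is randomized, and each surgeon does at least 5 cases with each, so a team's general timing habits are not tied to one arm. Equal error in both arms adds noise, not bias. This stands for habits that do not depend on the device. It does not cover timing that changes with the known device or with its release.
- **No mechanism is documented.** The documents give no release time for either stapler and do not describe what EASY/THICK MODE does mechanically. The line may also be brought into view during the count, so the timing and whole-line rules need not conflict. This stands: the difference is a possibility only.
- **Not everything depends on the 10-second image.** Bleeding that needs control before the last firing is photographed separately, and that image is also considered. This stands, and it limits how much severe early bleeding could be missed.
- **Departing from the count is a protocol deviation.** True, but with no time recorded a departure would rarely be recognized.

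A reader might also infer that one arm could lose 10% to 50% of its time to bleed. The documents do not support that for the whole line, for the reason shown in the first illustration.

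**Conclusion.** The gap is real but limited. Capture of the primary-outcome image is timed by an unrecorded count, from an imprecise start, by someone not stated to be masked. A difference between arms in that interval is possible, and the planned data could neither detect it nor correct for it.

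A reader might go further and conclude that the comparison is biased. The documents do not support that: they contain nothing to show that timing will differ by arm.

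No whole-line magnitude can be given. The percentages and error rates in the working rest on assumed firing intervals, bleeding rates and delays, and only show that the answer depends on facts the plan does not collect.

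This is a worthwhile, inexpensive improvement rather than a defect that invalidates the design. The argument for making it is that the interval cannot be reconstructed from the planned forms afterwards. If timing proves equal, the record lets the sponsor demonstrate it.

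**What to change.** In Steps and Procedures:

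- Define time zero as jaw release after the last firing.
- Replace the count with a timer or the saved laparoscope recording.
- Score the first frame at or after 10 seconds that shows the entire staple line, chosen by that rule in both arms. This settles which requirement gives way when the line is not fully in view at 10 seconds, and removes discretion over the frame.
- Remove any clock display or device cue from the image before it goes to the evaluator.

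On Appendix A, add one field for the actual elapsed seconds from time zero to the scored frame.

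In the analysis, report elapsed time by arm and keep all cases in the primary analysis. Dropping cases outside a timing tolerance could remove them non-randomly from only 30 per arm.

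The cost is a few sentences of protocol text, a short recording and one extra field per case. The change concerns image capture only and leaves the surgeon's discretion over bleeding control as it is.

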The Principal Investigator reserves the right to terminate the study in the interest of subject welfare. The Sponsor may terminate the study for administrative reasons.

Should the study be terminated, all documentation pertaining to the study must be returned to the Sponsor. Any actions required to assess or maintain study subject safety will continue as required, despite termination of the study by the Sponsor.

Protocol Deviations:

Deviations from the protocol will be assessed as "minor" or "major" in agreement with the Sponsor. Major deviations from the protocol may lead to the exclusion of a subject from data analysis and will be considered on a case-by-case basis.

The Investigator will not deviate from this protocol for any reason without prior written approval from the Sponsor, except in cases of medical emergencies. The Investigator may deviate from the protocol without prior approval only when the change is necessary to eliminate an apparent immediate hazard to a subject. In that event, the Investigator will notify the Sponsor immediately by phone, notify the IRB, and confirm notification to the Sponsor in writing within 5 working days after the change is implemented.

Statistics:

This is an open-label study. Formal sample size calculations were not performed. The number of subjects was chosen based on feasibility and is considered sufficient to meet the study objectives.

Detailed methodology for summary and statistical analyses of the data collected in this study will be documented in the Clinical Study Report.

Direct Access to Source Data/Documents:

The Principal Investigator will ensure that the Sponsor, IRB, and regulatory authorities will have direct access to all study sites, source data/documents, and reports for the purpose of monitoring and auditing. In the event that other study-related monitoring should be done by other parties, those parties will be required to sign a confidentiality agreement prior to any monitoring or auditing.

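### The extra-image rule stops at the last firing and no form records control of bleeding, so a treated staple line can be scored as dry and a missed image cannot be detected

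*Combined protocol and SAP*

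**What the plan says.** The Primary Outcome Measure section defines the outcome as: "Incidence of intraoperative staple line bleeding as measured by the provided bleeding severity scale". Under Steps and Procedures, a third-party evaluator, blinded to surgeon and device, scores photographs sent by the research coordinator. No other clinical information is described as going to the evaluator. The Summary states that investigators are not masked.

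Steps and Procedures governs treatment of the line in three places:

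- Restriction: "No sutures, cautery or clips shall be applied to the staple line during stapling, unless required". The sentence goes on to leave this to the surgeon.
- Routine image: taken after a 10-second count following the last firing.
- Extra image: "In the event that bleeding from the staple line requires control prior to the last firing, an additional image should be captured". It is to be taken before the control is applied. Where a case has several images, the evaluator takes all of them into account.

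Appendix A, the Data Collection Sheet, has two items under intraoperative outcomes: product malfunction and transfusion due to staple line bleeding. Appendix B has a date, the evaluator, the case ID and one score from 1 to 5. On sample size, the Statistics section says: "Formal sample size calculations were not performed". It leaves the analysis methods to the Clinical Study Report.

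**The concern.** What the evaluator can score depends on what the camera saw, and that depends partly on a decision by a surgeon who knows which stapler is in use. If a bleeding line is controlled before any image exists, the photograph may show a dry line and the case may enter the primary outcome as no bleeding. Masking the evaluator protects the reading of the image. It does not protect the decision that shaped the image.

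If such cases occurred more often with one stapler, they would create or hide a difference between devices. If they occurred equally in both arms, they would shrink a real difference. Without a field recording control, neither effect could be measured afterwards from the study forms.

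**Working it through.** The plan gives no expected rates, alpha, power or test, so there is no planned figure to reproduce. The check has two parts.

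**1. The rules set side by side**

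| When the line is treated | Image before control asked for? | Control recorded on a form? | Result |
|---|---|---|---|
| Before the last firing, extra image taken | Yes | No | Evaluator sees the untreated line; outcome protected |
| Before the last firing, extra image missed | Yes, but not done | No | May be scored 1; the forms cannot show the omission |
| Between the last firing and the routine image | No | No | May be scored 1 with the plan followed as written |

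The third row is a gap in the rule. The second is non-adherence that the data cannot reveal: a case with one image may be a dry line or a treated line whose extra image was not taken.

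**2. Size, under assumptions**

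From the protocol: 30 cases per arm. Assumed: true incidence p = 40% in both arms, a pooled chi-square test at two-sided 5%, and a share h of bleeding cases lost (treated, then photographed dry) in one arm only.

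Observed incidence in the affected arm = p(1 − h). Bleeding cases lost in that arm = 30 × p × h, out of an expected 30 × 0.40 = 12.

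False-positive chance = sum over all pairs (a, b), each from 0 to 30, of Bin(a; 30, p) × Bin(b; 30, p(1 − h)), counting the pairs where the test rejects.

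| h | Observed rates | Expected cases lost | False-positive chance |
|---|---|---|---|
| 0 | 40% v 40% | 0 | 4.9% |
| 5% | 40% v 38% | 0.6 | 5.1% |
| 10% | 40% v 36% | 1.2 | 6.0% |
| 25% | 40% v 30% | 3 | 12% |
| 50% | 40% v 20% | 6 | 39% |

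- **Other true rates.** At h = 25% the chance is 7.9% for a true rate of 20% and 21.8% for 60%.
- **Other test.** With Fisher's exact test at a true 40%, it is 2.6% with no loss and 7.8% at h = 25%.
- **Equal loss in both arms.** For a true 50% v 20%, normal-approximation power is 69% with no loss, 62% at 10% loss (45% v 18%) and 55% at 20% loss (40% v 16%).
- **Single cases.** 15/30 v 7/30 gives Fisher p = 0.060, and 15/30 v 6/30 gives p = 0.029. One reclassified case can move a result across 5%.

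**The case against.** The strongest reply is that the plan already handles the main route. It restricts treatment during stapling, asks for an image before any control that precedes the last firing, and has the masked evaluator weigh every image. A missed image would be a deviation, to be graded under Protocol Deviations. The stage with no rule is nominally 10 seconds long. All of this stands, and it limits the weight of the point. What it does not answer is detection: the image is worded as something that should be taken, and the deviation process can act only on omissions that someone knows about.

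A reader might infer that control leaves no trace, so that a treated line can never be told from a dry one. The documents do not support that. An extra image, when taken, is itself a trace. The final image is meant to be clear and to show the whole line, so clips or sutures might be visible in it (an inference; cautery may be less so). Source documents are open to the sponsor, although the protocol does not say whether they record haemostasis or ask that they be used in scoring. What is missing is a data field.

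A reader might also want every treated line without a prior image counted as bleeding in the primary outcome. That would let an unmasked decision set the outcome and bypass the evaluator. A clip placed on a dry line would count as bleeding, and no level on the 1 to 5 scale would follow from it. That approach belongs in a sensitivity analysis.

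**Conclusion.** The point holds in a limited form. The image rule leaves one stage uncovered, between the last firing and the routine image. For earlier control the safeguard is real when followed, but nobody can verify from the study forms that it was followed.

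The size is unknown and may be small. With a true 40% in both arms, losing 5% to 10% of bleeding cases in one arm moves the false-positive chance only from 4.9% to between 5.1% and 6.0%. The 12% and 39% figures need a quarter or a half of bleeding cases to be lost in one arm and none in the other. A reader might take those as the expected effect, or conclude that the plan is biased toward one device. The documents give no basis for either, and differential control by an unmasked surgeon is a risk, not a finding. All figures rest on assumed rates and an assumed test.

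This is a cheap improvement to data capture. It is worth making before enrolment, because information not recorded at the case may not be reliably recoverable later.

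**What to change.** 1. **Image rule (Steps and Procedures).** Extend the sentence so that an image is captured before any control of staple line bleeding that precedes the final image, including control during the 10-second count.
2. **Appendix A.** Add one item: *Sutures, cautery or clips applied to the staple line before the final image? Yes/No. Reason: bleeding/other. Image taken beforehand? Yes/No.*
3. **Analysis.** Keep the masked evaluator's score as the primary outcome. Report the proportion of lines treated before the final image by arm. Add a sensitivity analysis of incidence in which a line treated for bleeding without a prior image counts as bleeding.

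The surgeon's discretion to treat is unchanged; only imaging, recording and analysis are affected.

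The cost is one amended sentence, a few more form entries per case on a sheet already completed after each operation, and a short analysis statement. The downside is that the treated and reason entries are unmasked reports, which is why they are used only in supportive and sensitivity analyses.

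### Major deviations may be dropped from the analysis case by case, with no criteria, timing or masking, in a randomised comparison with open-label investigators

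*Combined protocol and SAP*

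**What the plan says.** **Exclusion.** Protocol Deviations has deviations graded minor or major in agreement with the Sponsor. Neither grade is defined. A major deviation "may lead to the exclusion of a subject from data analysis and will be considered on a case-by-case basis". The section does not say when the decision is taken, or whether those deciding are kept unaware of the device or the bleeding score.

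**Limit on deviations.** The same section says: "The Investigator will not deviate from this protocol for any reason without prior written approval from the Sponsor, except in cases of medical emergencies". Removing an immediate hazard to a subject is also exempt from prior approval.

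**Withdrawal.** Under Withdrawal of Subjects, "subjects may be withdrawn from the study by the Principal Investigator in consultation with the Sponsor" for an adverse event, a protocol violation or loss to follow-up. Then: "Withdrawn subjects will be replaced, until 60 subjects complete the study". On early withdrawal, "all data normally collected by study completion should be collected at the time of premature discontinuation or at the scheduled discharge". Of the reasons for premature withdrawal, the section says "this information will be recorded in the Clinical Study Report".

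**Masking.** The Summary gives no masking for investigators. Only the evaluator who scores the images is masked, to surgeon and device.

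**Analysis.** Statistics says: "Detailed methodology for summary and statistical analyses of the data collected in this study will be documented in the Clinical Study Report". No analysis set is named in any section.

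**The concern.** Randomisation makes the two stapler groups comparable at the outset. That comparability is protected only if who is analysed does not depend on what happened after assignment. Here the decision to leave a subject out is discretionary, comes after the operation, and rests with people of whom at least the investigators know the device. Surgeons also see the bleeding directly, so they do not need the evaluator's score to know which cases bled. Masking the evaluator protects the scoring of an image. It does not protect the choice of which scored cases enter the comparison.

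Withdrawal raises a related but weaker question. Adverse event is a listed reason for withdrawal, and device-related adverse events are a secondary outcome. If withdrawn subjects were replaced and not analysed, some of the events the trial is meant to count could drop out of the count.

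**Working it through.** The plan has no figure to reproduce: Statistics says that no formal sample size calculation was done, and no bleeding, withdrawal or exclusion rate is given. The check is first a reading of the text, then an illustration.

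**Step 1. Is the exclusion rule limited elsewhere?** No. The prior-approval requirement reduces how often deviations occur, but it does not mask the approver and does not say who is analysed. The emergency and hazard exemptions could cover events related to bleeding.

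**Step 2. Who knows what?** Investigators know the device (Summary). That the Sponsor knows it too is an inference from the open-label design and from its access to records: the Sponsor, among others, "will have direct access to all study sites, source data/documents, and reports for the purpose of monitoring and auditing". No section says whether the evaluator's score reaches those who decide on exclusions.

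**Step 3. What does withdrawal put at risk?** The image is taken ten seconds after the last firing (Steps and Procedures). Participation ends after the one-month visit (Study Details). A subject withdrawn after surgery should therefore already have a primary image. The bleeding result is lost only if the analysis is restricted to completers. Leakage and device-related adverse events are recorded at one month (Appendix A) and are more exposed. For a rare outcome, one lost case is 1/30 = 3.3 points of an arm.

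**Step 4. Arithmetic illustration.** Input from Steps and Procedures: 30 per arm. Assumptions: the five-level scale is reduced to bleeding yes or no; true incidence p is 10%, 30% or 50%, equal in both arms; up to k cases are affected, all bleeders and all in one arm.

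Let X ~ Bin(30, p) be the bleeders in that arm and m = min(k, X) the number affected.

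- Excluded, not replaced: shift = E[(X − m)/(30 − m)] − p.
- Replaced and not analysed: shift = E[(X − m + Bin(m, p))/30] − p = −E[m](1 − p)/30.

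Exact enumeration gives, in percentage points:

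| p | k | mean affected | excluded | replaced |
|---|---|---|---|---|
| 10% | 1 | 0.96 | −2.96 | −2.87 |
| 10% | 3 | 2.36 | −7.64 | −7.09 |
| 10% | 5 | 2.89 | −9.56 | −8.67 |
| 30% | 1 | 1.00 | −2.41 | −2.33 |
| 30% | 3 | 3.00 | −7.77 | −6.99 |
| 30% | 5 | 4.96 | −13.83 | −11.57 |
| 50% | 1 | 1.00 | −1.72 | −1.67 |
| 50% | 3 | 3.00 | −5.56 | −5.00 |
| 50% | 5 | 5.00 | −10.00 | −8.33 |

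Hand check of one replaced entry: p = 10%, k = 5 gives 2.89 × 0.9/30 = 0.0867, or 8.67 points. Hand check of exclusion at the expected count: 9/30 = 30.0% becomes 6/27 = 22.2%, a drop of 7.8 points.

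Replacement restores the number of subjects but removes little of the shift. The same removal in both arms, or removal unrelated to bleeding, gives no expected difference. No type I error is quoted, because the plan names no test and the figure would depend on the removal model assumed.

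**The case against.** Four points on the other side have weight.

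1. *The obvious route from bleeding to exclusion is closed.* Steps and Procedures allows sutures, cautery or clips at the surgeon's discretion, asks for an extra image first, and has the evaluator consider all images. A reader might infer that a case needing haemostasis becomes a deviation and is dropped. The text does not support that: control of bleeding is not in itself a deviation. What stands is that the class of major deviations is left undefined.

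2. *The primary result survives withdrawal.* This is largely right. A reader might infer from the replacement rule that only the 60 completers will be analysed. The wording is compatible with that but does not say it, and data collection at withdrawal is required. The withdrawal half is therefore an unclear analysis set, not a stated removal.

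3. *The arithmetic is extreme.* Also right. No section supports the assumption that every affected case is a bleeder, or that all fall in one arm, or that as many as 5 of 30 are affected. The table shows sensitivity, not expected bias, and should not set the severity.

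4. *Methods will follow in the Clinical Study Report.* The missing analysis set is part of that wider deferral and should not be counted twice. The deferral does not require the rules to be fixed before outcomes are known. The exclusion clause is separate, because it is a rule the plan does state.

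**Conclusion.** The point holds, chiefly for the exclusion clause. Followed as written, the plan lets subjects be removed from a randomised comparison after the event, at discretion, with no masking required and with open-label investigators. That conclusion rests on the text and can be held with high confidence. It does not extend to saying that bias will occur: its existence, direction and size cannot be determined from the documents.

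The withdrawal rule is secondary. It mainly affects leakage and device-related adverse events at one month, and affects bleeding only if a completer analysis is adopted.

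The recording of withdrawal reasons is a partial safeguard, but no split by arm is stated, and no reporting of deviation exclusions is required. The change should be made because the gap is clear and costs little to close, not because of the worst-case figures.

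**What to change.** (a) Replace the exclusion sentence. The primary analysis should include all randomised subjects in whom a study stapler was fired, in the assigned arm, including withdrawn subjects and those with major deviations. Count and list by arm any fired case without a usable image, with a sensitivity analysis for the missing score. List by arm, with reasons, anyone randomised but not fired, because unmasked staff also make that decision.

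(b) Confine deviation exclusions to a per-protocol sensitivity analysis, with criteria listed in advance and applied without knowledge of the bleeding score and, where possible, of the device.

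(c) State that replacements are randomised in the same way, and that they add to, and do not substitute for, subjects already operated on. They serve mainly the one-month outcomes. Say how this fits with 30 per arm and the minimum of 5 operations per stapler for each surgeon.

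(d) Report withdrawals and exclusions by arm with reasons.

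The cost is protocol wording only. Deviating cases stay in the main result, a few analysed subjects will lack one-month data, and the analysed number may slightly exceed 60.
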